3.3.2. Recovery and Time to Recovery

The primary efficacy and one of the key secondary outcome measures is the time to recovery assessed through Day 29 + 6 days. Recovery will be defined as having a value of 1, 2, or 3 on the clinical status 8-point ordinal scale. The time to recovery will be defined as the elapsed time (in days) from randomization to the earliest day at which a subject reaches recovery. Note that since clinical status assessments are recorded as defined in Section 4.3, the day that is being assessed (not necessarily the day the response is collected) will be used to determine the timing of events. For example, a subject with a score of 5 recorded on Days 1-3 and a score of 3 recorded on

Day 4 will have a time to recovery equal to 3 days. It is also possible that a subject has a clinical status score > 3 reported for a particular day but was subsequently discharged on the same day. Such cases and other special cases will be reviewed by the Endpoint Review Committee or the NIAID Medical Officer, or her designee(s), to make the determination of whether the subject should be considered recovered in analyses. Subject data to be reviewed as part of this determination will include the reported clinical status scores while hospitalized, where the subject was discharged to (e.g. private residence, rehabilitation facility, long-term care/nursing home, comfort and care), and any information regarding readmittance. Subjects discharged to hospice or other end-of-life care will not be considered recovered. Additional information may be solicited to assess recovery.

Any subjects that are lost to follow-up or terminated early prior to an observed recovery will be censored at the day of their last observed assessment. Subjects who complete follow-up but do not experience recovery will be censored at the day of their Day 29 visit. All deaths that occur on or before Day 29 (and prior to any observed recovery) will be considered censored at 28 days. Note that we do not expect many subjects to worsen after discharge. However, we will evaluate whether any discharged subjects subsequently experience a worse clinical status and sensitivity analyses will be conducted accordingly. For these analyses, subjects who recover but are later readmitted for COVID-19 will not be considered a recovery but will instead be censored at 28 days.

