3.3.4. Time to Clinical Status Improvement

Additional analyses will evaluate the time to improvement of at least one point on the clinical status 8-point ordinal scale. That is, improvement will be defined as a decrease of at least one point on the 8-point scale compared to the baseline value (e.g. from 5 to 4; from 5 to 3) and the time to improvement will be defined as the elapsed time (in days) from randomization to the earliest day of observed improvement. Note that since clinical status assessments are recorded as defined in Section 4.3, the day that is being assessed (not necessarily the day the response is collected) will be used to determine the timing of events.

For analyses of this outcome, imputation of the clinical score may be performed following the rules described in Section 6.5.

Any subjects that are lost to follow-up or terminated early prior to an observed improvement will be censored at the day of their last observed assessment. Subjects who complete follow-up but do not experience improvement will be censored at the day of their Day 29 visit. All deaths that occur on or before Day 29 (and prior to any observed improvement) will be considered censored at 28 days.

An alternative definition of improvement will also be used where improvement will be defined as a decrease of at least two points on the 8-point scale compared to the baseline value (e.g. from 5 to 3; from 5 to 2). The timing and censoring definitions will follow similarly to the above.

3.3.5. Time to Discharge or NEWS of ≤ 2

The time to discharge or NEWS of ≤ 2 will be defined as the elapsed time (in days) from baseline to the earliest day at which either of the following occur:

- Discharge from hospital, unless discharged to hospital or end-of-life care.
- Reported NEWS of ≤ 2 which is maintained for 24 hours

For the latter bullet, to meet this criterion, scores of ≤ 2 must be reported on consecutive study visits. The timing of the event will be set to the day of the second assessment. Subjects who enroll with a baseline NEWS of ≤ 2 must be discharged from the hospital to meet this endpoint.

All deaths or discharge to hospice or other end-of-life care that occur before discharge or before an observed NEWS of ≤ 2 will be considered censored at 28 days.

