4.3. Efficacy and Safety Variables

For each study day while the patient is hospitalized, the clinical status will be recorded on an 8-point ordinal scale as follows:

- Day 1 – The clinical assessment at the time of randomization.
- Day 2 + - The most severe assessment occurring from midnight to midnight (00:00 to 23:59) of the prior day (e.g., the value recorded on Day 3 will be the most severe outcome that occurred on Day 2).

where the clinical status scale is defined as follows:

8. Death;
7. Hospitalized, on invasive mechanical ventilation or ECMO;
6. Hospitalized, on non-invasive ventilation or high flow oxygen devices;
5. Hospitalized, requiring supplemental oxygen;
4. Hospitalized, not requiring supplemental oxygen- requiring ongoing medical care (COVID-19 related or otherwise);
3. Hospitalized, not requiring supplemental oxygen - no longer requires ongoing medical care;
2. Not hospitalized, but new or increased limitation on activities and/or requiring new or increased home oxygen;
1. Not hospitalized, no limitations on activities

A modified version of the ordinal scale will be used in sensitivity analyses of the primary and secondary outcomes. The modified scale will be as follows:

8. Death;
7. Hospitalized, on invasive mechanical ventilation or ECMO;
6. Hospitalized, on non-invasive ventilation or high flow oxygen devices;
5. Hospitalized, requiring supplemental oxygen;
4. Hospitalized, not requiring supplemental oxygen- requiring ongoing medical care (COVID-19 related or otherwise);
3. Not hospitalized, but new or increased limitation on activities and/or requiring new or increased home oxygen;
2. Hospitalized, not requiring supplemental oxygen - no longer requires ongoing medical care; or Not hospitalized, no limitations on activities.

That is, category 1 and 3 of the original scale will be combined into the lowest category. This scale will be denoted as the “Modified Recovery” ordinal scale.

In review of study data and site data queries for ACTT-3 subjects who received study product after reaching ordinal score 6, the study team identified that there was ambiguity in the high-flow oxygen categorization. The language in the MOP allowed for different interpretation of high-flow oxygen use, where some clinical sites interpreted and entered any high-flow device use as Ordinal Score 6 while other sites used less than 15L on a high-flow device and entered this as Ordinal Score 5.

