8.2.1. Ordinal Scale Outcomes (Key Secondary Outcome Measure)

For the analysis of the first key secondary outcome measure, the distribution of the 8-point ordinal clinical status scale with 8 categories at Study Visit Day 15 (not necessarily actual study day 15), the outcome will be analyzed using a proportional odds model with treatment arm and disease severity as covariates. The treatment odds ratio estimated from the model will be presented along with the p-value ([Table 18](#) and [Table 19](#)). The analysis will be repeated using the modified oxygen use scale. The Study Visit Day 15 clinical status score will be depicted graphically using shifted bar plots; the outcomes will be presented by baseline ordinal score and treatment group ([Figure 11](#)). In addition to the subgroup analyses, the main analysis will be repeated including a treatment * baseline ordinal score interaction term, where the interaction term p-value will be reported for the interaction model.

Multiple supplemental analysis of this key secondary outcome will be performed. Time to improvement by at least one category in the clinical status 8-point scale (see Section [3.3](#)). The log rank test will be performed using a Cox proportional hazards model to test whether the curves differ between treatment arms. The median time to event and CI in each treatment group will be summarized along with the treatment hazard ratio estimate and log rank p-value ([Table 20](#)). Differences in time-to-event endpoints by treatment arm will be summarized with

Kaplan-Meier curves ([Figure 12](#)). Number at risk, hazard ratio and log rank p-values will be presented on the figures. The analyses (and tabular and graphical summaries) will be repeated using the outcome of time to improvement in two categories of the ordinal scale defined in [Section 3.3](#).

The above analyses will be repeated with the Modified Recovery ordinal scale described in [Section 4.3](#) ([Table 21](#)). The only subgroup analysis that will be performed for time to improvement will be an analysis that classifies subjects by the duration of symptoms at baseline subgroups (above/below the median) ([Table 22](#)).

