proc lifetest data=enrevent plots=(rmst) method=breslow rmst(cl);
by stratum;
time evntday * Censor(1);
strata trtcode /diff=all;
ods output rmst=rmst;
run;
```

Stratified by Baseline Ordinal Score (“Any Baseline Ordinal Score” row).

```
proc lifetest data=enrevent plots=(rmst) method=breslow rmst(cl);
time evntday * Censor(1);
strata trtcode CRSEVERE /diff=all;
ods output rmst=rmst;
run;
```

Table 17: Summary of Recoveries and Deaths by Day 29 – mITT Population

Grouping Variable	Baseline Ordinal Score	Treatment Group	Recovered		Did Not Recover		Deaths		Not Recovered or Died		
			n	%	n	%	n	%	n	%	
Baseline Ordinal Score	4	Interferon beta-1a + RDV (N=X)	x	x	x	x	x	x	x	x	
		Placebo + RDV (N=X)	x	x	x	x	x	x	x	x	
	5	Interferon beta-1a + RDV (N=X)	x	x	x	x	x	x	x	x	
		Placebo + RDV (N=X)	x	x	x	x	x	x	x	x	
	6	Interferon beta-1a + RDV (N=X)	x	x	x	x	x	x	x	x	
		Placebo + RDV (N=X)	x	x	x	x	x	x	x	x	
	Any Baseline Ordinal Score	Interferon beta-1a + RDV (N=X)	x	x	x	x	x	x	x	x	
		Placebo + RDV (N=X)	x	x	x	x	x	x	x	x	
	Any Baseline Ordinal Score (4 or 5)	Interferon beta-1a + RDV (N=X)	x	x	x	x	x	x	x	x	
		Placebo + RDV (N=X)	x	x	x	x	x	x	x	x	
Repeat for Modified Oxygen Use ordinal scale (Section 4.3) and duration of symptoms categories in Section 6.4											
N= Number of subjects in the mITT Population.											

Programming Note: For the categories of “Recovered”, “Did Not Recover” and “Deaths”, subjects who recover but subsequently die will be classified under “Recovered” and “Deaths”. If there are cases of this, a footnote will be added that states “Counts of recoveries and deaths include X subjects who recovered but subsequently died.”

Table 18: Odds Ratio for Better (Lower) Clinical Status Score at Study Visit Day 15 by Treatment Using a Proportional Odds Model, Interferon beta-1a + RDV Relative to Placebo + RDV – mITT Population

Analysis/Subgroup	Treatment Group	Odds Ratio		P-value
		Estimate	95% CI	
Main Analysis of Key Secondary Endpoint				
Analysis of Key Secondary Endpoint ^a	Interferon beta-1a + RDV (N=X)	x.xx	x.xx, x.xx	0.xxx
	Placebo + RDV (N=X)			
Analysis of Key Secondary Endpoint using Modified Oxygen Use Scale				
Analysis of Key Secondary Endpoint ^b	Interferon beta-1a + RDV (N=X)	x.xx	x.xx, x.xx	--
	Placebo + RDV (N=X)			
Subgroup Analyses of Key Secondary Endpoint^c				
[Repeat for each Section 6.4 subgroups]	Interferon beta-1a + RDV (N=X)	x.xx	x.xx, x.xx	--
	Placebo + RDV (N=X)			
Medications of Interest Subgroup Analyses^c				

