Any Medication of Interest ^d	Interferon beta-1a + RDV (N=X)	x.xx	x.xx, x.xx	--
	Placebo + RDV (N=X)			
Hydroxychloroquine/Chloroquine	Interferon beta-1a + RDV (N=X)	x.xx	x.xx, x.xx	--
	Placebo + RDV (N=X)			
Corticosteroids	Interferon beta-1a + RDV (N=X)	x.xx	x.xx, x.xx	--
	Placebo + RDV (N=X)			
Anti-Inflammatory Drugs	Interferon beta-1a + RDV (N=X)	x.xx	x.xx, x.xx	--
	Placebo + RDV (N=X)			
Covariate-Adjusted Model^c				
Covariate-Adjusted	Interferon beta-1a + RDV (N=X)	x.xx	x.xx, x.xx	--
	Placebo + RDV (N=X)			
Interaction Models				
Treatment-Baseline Ordinal Score Interaction (4 or 5 vs. 6)	Interferon beta-1a + RDV (N=X)	x.xx	x.xx, x.xx	--
	Placebo + RDV (N=X)			
Treatment-Continuous Baseline Ordinal Score (4 or 5) Interaction	Interferon beta-1a + RDV (N=X)	x.xx	x.xx, x.xx	--
	Placebo + RDV (N=X)	x.xx	x.xx, x.xx	
Treatment-Categorical Baseline Ordinal Score (4 or 5) Interaction	Interferon beta-1a + RDV (N=X)	x.xx	x.xx, x.xx	--
	Placebo + RDV (N=X)	x.xx	x.xx, x.xx	

^aAnalysis of key secondary endpoint using those subjects in the mITT Population with baseline ordinal score (actual score) of 4 or 5 with disease severity as a model covariate.

^bThis analysis used a modified version of the ordinal scale where the definitions of categories 5 and 6 are, respectively, “Hospitalized, requiring supplemental oxygen or high flow oxygen devices at oxygen flow rate less than or equal to 15L/min” and “Hospitalized, on non-invasive ventilation or high flow oxygen devices at oxygen flow rate greater than 15L/min”.

^cRestricted to subjects with baseline ordinal score of 4 or 5.

^dExcluding statins, ARBs, and AECIs.

Odds ratios for interaction models are calculated at the level of each individual OS category.

Programming Notes:

For the Main Analysis, the p-value will only be reported if the p-value from the primary analysis of time to recovery (including all three OS strata) is significant. If the p-value will not be reported, then the columns will be removed.

Apart from the “Treatment-Baseline Ordinal Score Interaction (4 or 5 vs. 6)” model, all analyses will be restricted to subjects with a baseline ordinal score of 4 or 5.

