As Treated Population	6	Interferon beta-1a + RDV (N=X)	x	x.x	x.x, x.x	x.xx	x.xx, x.xx
		Placebo + RDV (N=X)	x	x.x	x.x, x.x		

N = Number of subjects in the specified treatment group, analysis population, and baseline ordinal score group.
 
n = Number of subjects with improvement.
 
HR is the ratio of the hazard of improvement in each treatment group estimated from the Cox model. The ratio is Interferon beta-1a + RDV to Placebo + RDV.
							

Tables with similar format:

Table 21: Time to Improvement on the 8-Point Ordinal Scale by Treatment Group: Modified Recovery Ordinal Scale**Table 22: Time to Improvement on the 8-Point Ordinal Scale by Treatment Group and Duration of Symptoms at Baseline – mITT Population**

Programming notes for Table 21:

The table will include the footnote: This analysis used a modified version of the ordinal scale where the categories “Hospitalized, not requiring supplemental oxygen - no longer requires ongoing medical care” and “Not hospitalized, no limitations on activities” were classified together and given a score of 2 while the category “Not hospitalized, but new or increased limitation on activities and/or requiring new or increased home oxygen” was given the score 3.”

Programming notes for Table 22:

The “Analysis Population” column will be re-labeled “Duration of Symptoms at Baseline”. The “Baseline Ordinal Score” column will be removed. Rows will be generated for each subgroup defined by duration above/below the median. Only subjects with baseline ordinal score 4 or 5 will be included in the table. The footnote for “N” will read “N = Number of subjects in the specified treatment group and analysis population with a baseline ordinal score of 4 or 5.”

Table 23: Clinical Status Scores by Treatment Group and Study Visit – mITT Population, Baseline Ordinal Score of 4 or 5

Study Visit	Ordinal Scale Measure	Interferon beta-1a + RDV (N=X)			Placebo + RDV (N=X)			Risk Difference	
		n	%	95% CI	n	%	95% CI	%	95% CI
Day 1	Death at or before Study Visit (8)	x	x	x.x, x.x	x	x	x.x, x.x	x.x	x.x, x.x
	Hospitalized, on invasive mechanical ventilation or ECMO (7)	x	x	x.x, x.x	x	x	x.x, x.x	x.x	x.x, x.x
	Hospitalized, on non-invasive ventilation or high flow oxygen devices (6)	x	x	x.x, x.x	x	x	x.x, x.x	x.x	x.x, x.x
	Hospitalized, requiring supplemental oxygen (5)	x	x	x.x, x.x	x	x	x.x, x.x	x.x	x.x, x.x

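### Most of the Modified Recovery sensitivity analysis must reproduce the main result by construction, and no output on that scale is specified for the Day 15 key secondary endpoint, where the re-ordering does matter

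*SAP*

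**What the plan says.** SAP 4.3 defines the Modified Recovery scale and gives its scope: "A modified version of the ordinal scale will be used in sensitivity analyses of the primary and secondary outcomes". The re-coding is summarised as "That is, category 1 and 3 of the original scale will be combined into the lowest category". Original category 2 (at home with limitations or home oxygen) becomes the next category up, and categories 4 to 8 keep their values.

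The outcomes it could be applied to are defined in SAP 3.3:

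- Primary (3.3.2): "Recovery will be defined as having a value of 1, 2, or 3 on the clinical status 8-point ordinal scale".
- Time to improvement (3.3.4): "improvement will be defined as a decrease of at least one point on the 8-point scale compared to the baseline value", with a second version that needs two points.

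On what will be run:

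- SAP 8.1.2 repeats the primary analysis on a different scale, Modified Oxygen Use (Table 11). It does not mention Modified Recovery.
- SAP 8.2.1 describes the Day 15 proportional odds model and repeats it on the modified oxygen use scale. It then describes time to one- and two-category improvement, and then says "The above analyses will be repeated with the Modified Recovery ordinal scale", citing Table 21.
- Table 21 covers time to improvement only. Its footnote says the two merged categories "were classified together and given a score of 2".
- Table 18 has a block headed "Analysis of Key Secondary Endpoint using Modified Oxygen Use Scale" and none for Modified Recovery. Table 19 has the same format.

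**The concern.** The scale exists to test whether conclusions depend on how two states are ranked: in hospital but no longer needing care, and at home with limitations. If Table 21 matches Table 20, a reader will take that as evidence that the ranking is unimportant. For most of the table the match is guaranteed whatever the treatment does, so it carries no information.

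The Day 15 ordinal outcome is a key secondary endpoint, and its odds ratio does use the order of categories 1 to 3. Modified Oxygen Use cannot stand in for the missing check, because it only moves the border between categories 5 and 6.

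**Working it through.** **Step 1: the mapping (SAP 4.3).** Original to modified: 8→8, 7→7, 6→6, 5→5, 4→4, 3→2, 2→3, 1→2. Eligible baselines are 4, 5 and 6, and none of them changes value.

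**Step 2: which original categories count as the event under each scale.**

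| Outcome | Baseline | Original scale | Modified scale | Same? |
|---|---|---|---|---|
| Recovery | any | {1,2,3} | {1,2,3} | yes |
| At least 1 category | 4 | {1,2,3} | {1,2,3} | yes |
| At least 1 category | 5 | {1–4} | {1–4} | yes |
| At least 1 category | 6 | {1–5} | {1–5} | yes |
| At least 2 categories | 4 | {1,2} | {1,3} | **no** |
| At least 2 categories | 5 | {1,2,3} | {1,2,3} | yes |
| At least 2 categories | 6 | {1–4} | {1–4} | yes |

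**Step 3: count in the table as laid out.** The Table 20 shell, which Table 21 copies, has 2 thresholds × 2 baseline groups (4 or 5; 6) × 2 populations (mITT; As Treated) = 8 hazard ratios. Only two-category improvement in the 4-or-5 group can move: 1 × 1 × 2 = 2. The other 8 − 2 = 6 must equal Table 20.

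**Step 4: one wording exception.** In SAP 6.5 the original-scale rule imputes a 2 at discharge but excludes discharge to hospice or other end-of-life care. The modified-scale rule imputes a 3 and does not repeat that exclusion. Read literally, a hospice discharge could count as improved on the modified scale only. That difference has nothing to do with ranking.

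**Step 5: the Day 15 model.** I first reproduced the plan's own figure. Protocol Appendix C 9.2 gives N = 12(z_{α/2}+z_β)² / [λ²(1−Σp_i³)]. For Scenario 1 (control 2/1/2/7/8/10/30/40%), odds ratio 1.75 and 85% power, Σp_i³ = 0.127, so N = 12(1.960+1.036)² / [0.5596² × 0.873] = 394, against 396 stated. The other scenarios give 417, 399, 368 and 358 against 419, 401, 370 and 360.

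Re-ordering leaves five cut-points untouched (those above 3) and replaces the two lowest by one. For Scenario 1, with the treatment column of protocol Appendix C Table 10 (1.2/0.6/1.2/4.3/5.3/7.2/26.5/53.8):

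- Original lowest cut (category 1 against worse): control 60/40, treatment 46.3/53.8; odds ratio (60/40)/(46.3/53.8) = 1.74.
- Modified lowest cut (original 1 or 3 against worse): control 50/50, treatment 39.1/61.0; odds ratio (50/50)/(39.1/61.0) = 1.56.

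The fitted common odds ratio over all cuts is 1.74 on the original scale and 1.60 on the modified scale. With an exact true odds ratio of 1.75, the fitted modified-scale values for Scenarios 1 to 5 are 1.61, 1.58, 1.58, 1.51 and 1.55.

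The affected categories hold most patients. In the five control scenarios, categories 1 to 3 together make up 80, 90, 85, 73 and 58%.

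**Step 6: a related duplicate.** Table 18 lists "Treatment-Continuous Baseline Ordinal Score (4 or 5) Interaction" and a categorical counterpart, both restricted to scores 4 and 5. With two levels, a linear term and an indicator are the same model with the same interaction p-value.

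**The case against.** Several stronger readings are tempting, and the documents do not support them.

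- *Day 15 is the only place the re-ordering matters.* It is not. Two-category improvement from baseline 4 also changes, and Table 21 does run it within the 4-or-5 group, the only group still enrolling. Table 21 is therefore not wholly empty.
- *The SAP leaves Day 15 out.* That is too firm. The sentence in 8.2.1 follows both the Day 15 model and the time-to-improvement text, and 4.3 covers secondary outcomes. Read broadly it could include Day 15, and SAP 17 allows extra tables. What can be said is that no Day 15 output on this scale is specified.
- *The primary result gets false support.* No primary output on this scale is specified in 8.1.2 or the shells. The mention of the primary outcome in 4.3 looks like loose drafting.
- *The modified scale could reverse the Day 15 result.* It could if treatment did nothing but move patients from category 3 to category 2, but that effect is invented. Under the protocol's own assumption the direction holds and the odds ratio is moderately smaller.

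Two larger remedies also go too far. Cutting Table 21 to baseline 4 would conflict with 8.2.1, which allows only the symptom-duration subgroup for time to improvement. Refitting the Table 18 interactions on scores 4 to 6 is debatable, because the key secondary analysis is restricted to 4 and 5.

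It is also fair to say that Table 21 is supplemental, its shell has no p-value column, and it plays no part in the testing rules of SAP 6.8. That lowers the stakes. It does not make guaranteed agreement informative, nor does it supply the missing Day 15 row.

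**Conclusion.** The point holds as a limited one. Of the eight hazard ratios in Table 21, six must equal Table 20 once the hospice wording is aligned, and time to recovery could not change if it were run. Among the specified outputs, the scale is informative only for two-category improvement in the 4-or-5 group, through baseline-4 subjects. The Day 15 odds ratio does respond to the re-ordering (1.74 against 1.60 in Scenario 1; 1.51 to 1.61 across scenarios for a true 1.75) but has no specified output.

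The identities follow from the SAP definitions alone. The odds ratios are illustrations: they rest on the protocol's assumed control distributions and on proportional odds at 1.75 on the original scale. The primary result is unaffected, so this is a change to consider rather than one the trial depends on.

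**What to change.** 1. In SAP 8.2.1 and Tables 18 and 19, add a row repeating the Day 15 proportional odds model on the Modified Recovery scale in baseline scores 4 or 5.
2. Add a footnote to Table 21 naming the rows that equal Table 20 by construction and saying they are not evidence of robustness.
3. In the SAP 4.3 sentence on scope, delete the word *primary*.
4. In SAP 6.5, add the hospice and end-of-life exception to the modified-scale discharge imputation.
5. Minor: in Table 18, drop one of the two identical interaction models on scores 4 and 5.

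The cost is wording plus one extra model fit per population on data already collected. The downside is one more row in each of Tables 18 and 19.
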